#### **5.5 Analysis Plan for Additional Secondary Objectives**

- Descriptive statistics will be presented for post-index overall RA related direct healthcare resource utilization (Excel Table 8)

- Consultations/visits to healthcare professionals for treatment of RA (number of patients with  $\geq 1$  visit; categorized by the treatment department listed in 3.5.4)
- Procedures received when visiting the healthcare professional(s) for treatment of RA (number of patients with  $\geq 1$  procedure; categories listed in 3.5.4)
- surgeries received when visiting the healthcare professional(s) for treatment of RA (number of patients with  $\geq 1$  surgery; categories listed in 3.5.4)
- Hospitalizations in relation to RA (number of patients with  $\geq 1$  admission)
- Length of stay in days (mean, SD, median)
- Concomitant medications taken for RA (number of patients with  $\geq 1$  medication; categories listed in 3.5.4))

- Associations between disease severity (measured by DAS28) and PROs (HAQ DI score, SF-36 domain scales, EQ-5D-3L index, WPAI outcomes) will be analyzed using the bivariate linear regression model (Excel Table 9.1). Separate models will be estimated to identify the association between DAS28 and each of the PROs.
- Additionally, in Excel Table 9.2, separate bivariate liner regression models will be estimated to identify the association between change in DAS28 and change in each of the PROs at 12 and 24 weeks after baseline respectively.

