4.0 Abstract

Title: Real-World Outcome of Rheumatoid Arthritis Patients in Korea on adalimumab (ROCKA Study).

Rationale and Background: Given the requirement to keep a balance between effectiveness and cost containment to ensure that the available health resources are used in a cost-effective manner, there is an increasing demand for real-world evidence (RWE) from policy makers, regulators, providers and payers in the region to optimize spending and patient outcomes.

So far, there are no data available regarding adalimumab's impact on patients' quality of life (QoL) and healthcare resource utilization (HCRU) in a realistic study design in Korea.

The goal of this study is to determine the QoL, HCRU and costs of the patients care in subjects with RA who are treated with adalimumab in Korea.

Results from study on the effect of adalimumab on Work Productivity and Activity Impairment (WPAI) scores and other Patient-Reported Outcomes (PROs) will be of interest to a variety of stakeholders in the healthcare system including patients, healthcare practitioners and payers in Korea.

Research Question and Objectives: The objective of this non-interventional, observational study is to assess the effect of adalimumab on health-related QoL and work productivity in patients with Rheumatoid Arthritis (RA) in Korea. Specifically, to achieve the above objective the following concrete steps will be taken:

1. Recruit investigators who are willing and able to recruit and follow new adalimumab users for 6 months follow-up
2. Collect the patients' clinical profile, patient-reported QoL, functioning, work productivity, treatment satisfaction and HCRU of RA patients at adalimumab initiation
3. Follow the patients initiating adalimumab for 24 weeks and identify the changes in clinical, economic, and PROs associated with adalimumab

Study Design: The study is designed as a prospective, observational study to assess the effect of adalimumab on health-related QoL and work productivity in patients with RA in Korea.

Note: This study is non-interventional and the subjects/investigators will follow the current clinical practice in each site and also the routine clinical follow up as determine by the treating physician.

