9.2.4.6 Data Collection

IMS will coordinate data collection with each site. At study initiation (Baseline, D0), patients will be asked to provide their written informed consent. The patient then will complete the study questionnaires in paper form. At all follow up visits (week 12 and 24), the patient will complete the study questionnaires while waiting for their appointment at their clinic, approximately 30 minutes before they visit their physicians. It is important that they complete the questionnaires prior to speaking with their clinician during the visit, as the clinician feedback might impact patient perceptions measured by the PRO instruments.

Patients must complete the survey by themselves without help from anyone. However, for patients who physically have difficulty filling out the questionnaires, help is allowed as long as there are no suggestions or discussion from the helpers. In addition, physicians will also be asked to complete a clinical CRF in paper form based on the patient's medical records at baseline, 12 weeks, and 24 weeks. The CRF completed by physicians will be returned to the study coordinator/nurse at each site as well.

All data filled in by the patient and physician will be collected at each site and returned directly to IMS. The data collection time is expected to be 10-13 months.

All patient and clinician data will be handled preserving confidentiality.

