9.7.6 Additional Secondary Endpoint Analysis

Additional efficacy analysis includes:

- Change in HAQ DI score at 24 weeks after the initiation of adalimumab, in those patients continuing on adalimumab, compared with those patients not continuing on adalimumab. The mean changes in these two groups will be compared using an independent t-test.
- Healthcare resource utilization will be described using number and percentage within each category (number of consultations, number of procedures received, number of surgeries, number of hospitalizations and length of stay, number of concomitant medications)
- Associations between disease severity and PROs
- Associations between change in disease severity and change in PROs

Exploratory endpoint

Change in patient satisfaction questions at weeks 12 and 24 after the initiation of adalimumab (observed population). These changes will be summarized as number and percentage of each response and compared with Kruskal-Wallis test. Satisfaction will also be dichotomized and analyzed over time with Cochrane-Armitage test for trends.

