### 2.3 Additional Secondary Objectives

- To describe the change in HAQ DI score at 24 weeks after the initiation of adalimumab, in those patients continuing on adalimumab (responder population), compared with those patients not continuing on adalimumab (non-responders). The mean changes in these two groups will be compared using an independent t-test.
- Patient's impression of change in RA at weeks 12 and 24 after the initiation of adalimumab, in those patients continuing on adalimumab (as observed population). Each response will be summarized as number and percentage.
- To summarize the healthcare resource utilization using number and percentage within each category (number of consultations, number of procedures received, number of surgeries, number of hospitalizations and length of stay, number and type of concomitant medications)
- To analyze the associations between disease severity and PROs (HAQ DI, SF-36 domain scales, EQ-5D-3L index, WPAI total lost productivity)
- To analyze the associations between change in disease severity and change in PROs (HAQ DI, SF-36 domain scales, EQ-5D-3L index, WPAI total lost productivity)

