## 3. STUDY DESIGN

### 3.1 Overview of Study Design

This study is designed as a prospective, observational study to assess the effect of adalimumab on health-related QoL and work productivity in patients with RA in China, South Korea, and Taiwan in clinical practice.

RA patients will be recruited from within the clinical settings of each rheumatologist participating in the study. Approximately 243 patients diagnosed with RA that meet the inclusion and exclusion criteria will be enrolled at approximately 26 sites in China, South Korea and Taiwan.

To assess health and disability outcomes, the HAQ DI will be assessed at baseline, Week 12 and Week 24 after treatment initiation with adalimumab. In addition, other PROs of work activity and well-being, including the WPAI, EQ-5D-3L, and SF-36, will also be assessed.

The patients identified by the recruiting investigators (specialty dependent on country/region; e.g. rheumatologist, internists, general practitioners, etc.) based on the study selection criteria will complete a set of patient questionnaires on QoL, functioning, work productivity, treatment satisfaction, impression of change and HCRU. Data will be captured at baseline (D0), Week 12 and Week 24.

The HCRU will also be collected. This includes surgical procedures, hospitalizations, bed days in hospital, physician consultations etc. Costs will be assigned based on the HCRU using standardized costs for each participating countries.

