### **3.5.4 Derived Variables**

- Number of consultations/visits to healthcare professionals for treatment of RA, categorized by the treatment department
  - ✓ General Practitioner (Taiwan: Family Medicine)
  - ✓ Rheumatologist
  - ✓ Gerontologist

- ✓ Orthopedist
  - ✓ Internist
  - ✓ Emergency department
  - ✓ Traditional Medicine
  - ✓ Physical therapist (Taiwan: Rehabilitation Medicine)
  - ✓ Other
- Number of procedures received when visiting the healthcare professional(s) for treatment of RA
  - ✓ Chest X-Ray
  - ✓ Spine X-Ray
  - ✓ Neck X-Ray
  - ✓ Shoulder X-Ray
  - ✓ Hand X-Ray
  - ✓ Knee X-Ray
  - ✓ MRI
  - ✓ CT scan
  - ✓ Electrocardiogram
  - ✓ Blood sample taken
  - ✓ Urine test
  - ✓ Endoscopy
  - ✓ Bone scan
  - ✓ Liver function test
  - ✓ Tuberculin Skin Test
  - ✓ Sputum tests
  - ✓ Other
- Number of surgeries received when visiting the healthcare professional(s) for treatment of RA
  - ✓ Arthroscopy
  - ✓ Carpal tunnel release
  - ✓ Cervical spinal fusion
  - ✓ Total knee replacement
  - ✓ Total hip replacement
  - ✓ Knee arthrodesis (fusion)
  - ✓ Hip arthrodesis (fusion)
  - ✓ Synovectomy
  - ✓ Other
- Number of hospitalizations in relation to RA

- Length of stay: total days in hospital in relation to RA
- Number of concomitant medications taken for RA
- Disease Modifying Antirheumatic Drug (DMARD)
  - ✓ Auranofin (Ridaura, Myochrysine)
  - ✓ Azathioprine (Imuran)
  - ✓ Cyclosporine (Sandimmune and Neoral)
  - ✓ Hydroxychloroquine (Plaquenil)
  - ✓ Leflunomide (Arava)
  - ✓ Methotrexate (Rheumatrex, Folex)
  - ✓ Minocycline (Minocin, Dynacin and Vectrin)
  - ✓ Sulfasalazine (Azulfidine)
  - ✓ Others

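### SAP 5.5 reduces every resource-use item except length of stay to patients with at least one event, although counts are promised and collected, and the SAP specifies no cost analysis although costs are part of the stated goal

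*SAP*

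**What the plan says.** The protocol abstract (section 4.0, Rationale and Background) sets the aim: "The goal of this study is to determine the QoL, HCRU and costs of the patients care in subjects with RA". SAP 3.1 adds: "Costs will be assigned based on the HCRU using standardized costs for each participating countries". Protocol 9.1 and the Study Design part of the abstract say the same in substance.

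The resource-use objective in SAP 2.3 calls for number and percentage within categories that are themselves quantities: "number of consultations, number of procedures received, number of surgeries, number of hospitalizations and length of stay, number and type of concomitant medications". Protocol 9.7.6 has nearly the same list. SAP 3.5.4 derives the matching variables, for example "Number of consultations/visits to healthcare professionals for treatment of RA, categorized by the treatment department".

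SAP 5.5 then sets out Table 8. For visits it asks for "Consultations/visits to healthcare professionals for treatment of RA (number of patients with" at least one visit, split by department. Procedures, surgeries, hospitalizations and concomitant medications follow the same pattern. Length of stay is the exception, with mean, SD and median.

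On timing, Protocol 9.2.4.6 says of the Week 12 and Week 24 visits that "the patient will complete the study questionnaires while waiting for their appointment at their clinic", about half an hour before seeing the physician. The follow-up questionnaire in Appendix J asks about use since the form was last completed.

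**The concern.** The plan promises volumes, collects volumes and derives volumes, and then tabulates a yes/no indicator. A patient with one visit and a patient with twelve count the same. For a service that nearly every patient in the study will use, the indicator sits at its ceiling whatever happens to use.

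Costing multiplies volumes by unit costs, so the indicator cannot feed a cost estimate, and no cost estimate is planned in any case. The protocol's rationale says that reimbursement in Korea depends heavily on local evidence on outcomes and economic endpoints. If the SAP is followed as written, the cost part of the goal has no planned output, and the resource-use part has one that discards most of the data.

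**Working it through.** No stated figure in the plan depends on this point, so there is none to reproduce. The check is a comparison of sections plus one illustration.

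**1. Each item from collection to report**

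| Item | Collected (Protocol Appendix J) | Derived (SAP 3.5.4) | Reported (SAP 5.5, Table 8) |
|---|---|---|---|
| Visits | times, per specialty | number, by department | patients with ≥1 |
| Procedures | times, per procedure | number | patients with ≥1 |
| Surgeries | up to five entries, with dates | number | patients with ≥1 |
| Hospitalizations | up to three entries, with dates | number | patients with ≥1 |
| Length of stay | days | total days | mean, SD, median |
| RA medications | drug, amount, frequency | number | patients with ≥1 |

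Five of the six items lose their counts at the last step.

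**2. The rheumatology line**

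- The Week 12 form is completed before the Week 12 consultation, so that consultation is not on it.
- The Week 24 form covers the time since the previous form, so the Week 12 consultation falls inside its period.
- Recruitment is from rheumatologists' clinics (SAP 3.1). A patient seen by the rheumatologist at Week 12 who returns an accurate Week 24 form therefore reports at least one rheumatology visit.

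**3. What the indicator hides**

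Inputs: 89 patients and 10% drop-out (Protocol 9.5), so completers = 89 × 0.9 = 80.1, about 80. Let each completer have the one built-in visit plus m further visits. The documents give no value for m; the range 0 to 12 is an assumption.

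Share with ≥1 visit = 80/80 = 100% for every m. Total visits = 80 × (1 + m):

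| m | Share with ≥1 | Total visits |
|---|---|---|
| 0 | 100% | 80 |
| 2 | 100% | 240 |
| 6 | 100% | 560 |
| 12 | 100% | 1,040 |

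The ratio of largest to smallest is 1,040/80 = 13, behind the same table entry.

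The built-in visit is not the whole explanation. Without it, and with visits taken as Poisson (also an assumption), the share with at least one is 1 − exp(−mean). This is 1 − exp(−4) = 98.2% at a mean of 4 and 1 − exp(−6) = 99.8% at a mean of 6. Any frequently used service comes close to the ceiling.

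**4. Costs**

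SAP section 6 lists twelve tables: 1, 2, 3.1, 3.2, 4, 5, 6, 7, 8, 9.1, 9.2 and 10. None is a cost table. SAP 3.5 has no cost variable, and SAP section 5 has no cost method, unit-cost source or price year.

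**5. Unequal follow-up**

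SAP 3.5 summarizes resource use over six months after baseline. Early leavers complete the resource-use items on the Early Termination Form, for a shorter period. At 10% drop-out that is 89 × 0.10 = 8.9, about 9 patients; at the SAP's own 13% of 100 per country it is 13. No denominator in patient-time is specified.

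**The case against.** The best defence is that the objective asks for number and percentage within each category, and patients with at least one event is a permissible reading of that. SAP 5.1 also says that continuous variables get mean, SD, median, minimum and maximum, and that tables may be modified. The full table shells are in a separate workbook that is not among the documents. Resource use is a descriptive, additional secondary objective. Costs appear in the abstract's goal and the design text, but not in Protocol section 8, the variable list in Protocol 9.3 or the objectives in SAP section 2.

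Some of this stands. The workbook's layout cannot be checked, and the primary endpoint is untouched. But the SAP 5.1 default applies only where nothing else is specified, and SAP 5.5 specifies something else. Leaving tables to be modified after results are seen is not a planned analysis. The workbook's tables are the ones listed in SAP section 6, where no cost table is named.

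The objection also rules out several stronger readings:

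- A reader might infer that Table 8 shows nothing but presence or absence. Length of stay is reported as a quantity.
- A reader might infer that volume cannot be determined. It can be computed from the collected counts; what is missing is its specification in Table 8.
- A reader might infer that all consultation lines are fixed near 100%. SAP 5.5 splits visits by department, and the built-in visit affects only the rheumatology line, for patients with the Week 12 consultation and the Week 24 form. Protocol 9.1 also mentions internists and general practitioners as recruiters. Lines for emergency visits, surgery and admission remain informative.
- A reader might infer that early leavers bias the percentages by a known amount. The documents give no basis for sizing that effect.

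**Conclusion.** The point holds in a limited form. As written, SAP 5.5 discards the counts for every resource-use item except length of stay, contrary to SAP 2.3 and 3.5.4. The rheumatology line carries almost no information on volume: in the illustration, a 13-fold range of total visits gives the same 100%. The cost part of the goal has no planned analysis at all.

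The ceiling argument assumes that the Week 12 consultation is with a rheumatologist and that the Week 24 form is completed accurately. The illustration assumes about 80 completers and the stated range of further visits. The conclusion on costs rests on the SAP text and its table list, without sight of the table shells. This is a reporting gap that can be closed from data already held, and it does not affect the HAQ DI analysis.

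**What to change.** In SAP 5.5 and Table 8, keep the count of patients with at least one event. Beside it, add for each category the events per patient (mean, SD, median, range) and the rate per patient-time on study, which allows for early leavers' shorter periods. The forms are dated, so the period each patient covers can be calculated.

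Add a note to the rheumatology line that it includes the Week 12 visit. Do not try to subtract scheduled visits: the form records one total per specialty and cannot separate them, and the study follows routine care, so those visits may be genuine use.

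Then settle costs one way or the other:

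- Specify a cost table, with the unit-cost source and price year. The documents name neither; they refer only to standardized costs.
- Or delete costs from the goal in Protocol 4.0 and remove the costing sentences in Protocol 4.0, Protocol 9.1 and SAP 3.1, so that no cost conclusion is drawn.

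The price is SAP wording and one or two more descriptive tables, plus an external unit-cost source if costing is kept. No new patient data are needed.

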## 5.6 Analysis Plan for Exploratory Objective

- In Excel Table 10, separate multivariate generalized linear models (GLM) will be estimated to test for the differential changes in primary and secondary efficacy outcomes after baseline, across the subgroups defined by the potential modifiers, including age, gender, baseline severity, and other diagnoses/comorbidities.

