9.5 Study Size

Approximately 89 patients diagnosed with RA will be recruited. The sample size was calculated by assuming an alpha of 0.05 and a power of 0.80 in a one-sided test, $Z(1-\alpha) = 1.645$ and $Z(1-\beta) = 0.842$. As to the primary variable, assuming a mean Δ HAQ-DI of -0.21 and a standard deviation (SD) of 0.5, according to the formula, 36 subjects are required. Then, given the importance of the secondary endpoint (WPAI), an improvement of 9.9 ± 25 hours of work time lost (mean=9.9, SD=25) requires 40 subjects. However, we assume a 50% employment rate in the study population and a drop-out rate of 10%, eventually approximately 89 patients will be required ($40/0.5/(1-0.1) = 89$).

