9.7.2 Analyzable population

All subjects who received at least one dose of adalimumab during the study will be included. The main analysis will be conducted on the pooled population, where appropriate, with each individual country analyzed separately as supportive data.

9.7.3**Planned Methods of Statistical Analysis**

All statistical tests will be two-tailed with a significance level of 0.05. Descriptive statistics will be provided. Descriptive analysis will be conducted on all key parameters and presented as mean, standard deviation, minimum, maximum, and median when continuous and as “n” and percent when categorical. Change from adalimumab initiation to 24 weeks will be calculated and evaluated for significant improvements using paired t-tests / ANOVA for parametric and Wilcoxon signed-rank for non-parametric data. Analysis will be also be conducted by severity level (moderate vs severe), disease duration quartile (to compare to prior work) and up to two (2) other subgroups. Cochran-Armitage test of trends or other similar methods may be used to compare categories of subjects.

9.7.4**Primary Endpoint Analysis**

The primary endpoint variable will be the change in HAQ DI score at 24 weeks after the initiation of adalimumab (observed population).

The objective of the primary endpoint analysis will be to demonstrate that treatment with adalimumab improves functioning as measured by the HAQ DI in subjects with RA following treatment initiation. This change will be summarized as the mean and 95% confidence interval and will be tested with a paired t-test.

The primary analysis will be summarized as the mean and 95% confidence interval and will be tested with a paired t-test without adjusting for baseline disease severity. For sensitivity analysis, the mean change in HAQ DI at Week 24 will be analyzed using ANOVA adjusting for baseline disease severity.

9.7.5**Secondary Endpoint Analysis**

The main secondary endpoint variable will be the change in HAQ DI at 12 weeks after the initiation of adalimumab.

The objective of endpoint analysis will be to demonstrate that treatment with adalimumab improves functioning as measured by HAQ DI in subjects with RA compared to baseline.

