9.7.8 Additional Analysis

Additional analysis will explore the potential modifying effects of baseline measures on the changes in primary and secondary efficacy outcomes. These measures will include age, gender, baseline severity, and other diagnoses/co-morbidities. The analysis will specifically test for differential changes across the subgroups defined by the potential modifiers using general linear models.

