## 5.2 Analysis Plan for Demographic and Clinical Characteristics

- Descriptive statistics will be presented for patient demographics (Excel Table 1), and clinical characteristics (Excel Table 2) for all patients by country. The following measures will be assessed as of the patient's baseline:
  - Patient age (mean, SD, minimum, maximum, median; categories: 18-34, 35-44, 45-54, 55-64, 65-74, 75+, missing)
  - Gender (male, female, missing)
  - Marital status (married, unmarried, missing)
  - Medical insurance type (National/Public insurance, Private insurance, Employer benefits, other, no insurance, missing)
  - Disease Activity Score in 28 joints - DAS28 (mean, SD, minimum, maximum, median; categories: Remission, Low Disease Activity, Moderate Disease Activity, High Disease Activity, Missing)
  - Number of patients with each of the comorbidities at baseline visit (See 3.5.2), and number of patients with any of these comorbidities

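### The effect-modifier models compare subgroups of age and baseline severity without giving cut-points; continuous terms would use the same data with more power if the relation is linear

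*SAP*

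**What the plan says.** Protocol 9.7.8 plans an exploration of effect modification by age, gender, baseline severity and comorbidity: "The analysis will specifically test for differential changes across the subgroups defined by the potential modifiers using general linear models". SAP 5.6 carries this into Table 10 as separate multivariate models testing differential change "across the subgroups defined by the potential modifiers, including age, gender, baseline severity, and other diagnoses/comorbidities". Neither section says how age or severity is coded.

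Groupings appear elsewhere:

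- **Severity.** Protocol 9.7.3 plans analyses "by severity level (moderate vs severe"), and SAP 3.5.2 puts the boundary at DAS28 5.1.
- **Age.** SAP 5.2 gives "categories: 18-34, 35-44, 45-54, 55-64, 65-74, 75+, missing" for the baseline descriptive table. SAP 3.5.2 lists both age at baseline and age groups among the independent variables.

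Both quantities are also collected as numbers: age in years on the baseline patient questionnaire, and the DAS28 score on the clinician form. In SAP 5.5 the score is the severity measure in the regressions for Tables 9.1 and 9.2: "Associations between disease severity (measured by DAS28) and PROs", with no grouping mentioned.

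**The concern.** Testing a numeric modifier through groups has two costs. A two-group cut discards the variation within each group. Several bands keep most of the variation but spread it over more degrees of freedom: six age bands need five, where a slope needs one. In a study expecting about 80 completers, and about half that for outcomes asked only of employed patients, either cost could hide a real gradient, and a null Table 10 might then be read as evidence of uniform benefit. Leaving the cut-points open adds a second risk, because they could be chosen after the data are seen. SAP 5.1 says the tables will be modified in the light of the analysis results.

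**Working it through.** **1. Numbers available.** Protocol 9.5 works "assuming an alpha of 0.05 and a power of 0.80 in a one-sided test". The one-sample formula is n = (SD × (1.645 + 0.842) / difference)².

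- HAQ DI: (0.5 × 2.487 / 0.21)² = 35.06, rounded up to 36. This matches "of -0.21 and a standard deviation (SD) of 0.5, according to the formula, 36 subjects are required".
- Work time lost: (25 × 2.487 / 9.9)² = 39.44, rounded up to 40. This matches "hours of work time lost (mean=9.9, SD=25) requires 40 subjects".
- Enrolment: 40 / 0.5 / 0.9 = 88.9, rounded up to 89, as stated.
- Completers: 89 × 0.9 = 80.1. Employed completers: 80.1 × 0.5 = 40.05.

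The check therefore uses n = 80, and n = 40 for the WPAI outcomes asked only of patients in paid work. SAP section 4 still carries 100 per country and 13% drop-out. That gives 100 × 0.87 = 87 completers and 43.5 employed, which changes little.

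**2. Formula.** The power of an F test at two-sided 0.05 (the level in Protocol 9.7.3) comes from the noncentral F distribution with noncentrality λ = n × R² / (1 − R²).

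- Continuous term: R² = ρ², 1 degree of freedom, where ρ is the correlation between modifier and change.
- Grouped term: R² = ρ² × k, with (groups − 1) degrees of freedom, where k is the share of a normal modifier's variance that the grouping keeps.

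Assumptions not given in the documents are a linear relation, the value of ρ, and the split. The values of k are 0.637 for a 50/50 split, 0.622 for 60/40, 0.576 for 70/30 and 0.490 for 80/20. For the six age bands k is 0.937, taking shares of 5, 15, 29, 30, 16 and 5%.

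**3. One case in full (n = 80, ρ = 0.3).**

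- Continuous: λ = 80 × 0.09 / 0.91 = 7.91 on 1 and 78 df; power 79.3%.
- Two groups, 50/50: R² = 0.09 × 0.637 = 0.0573, λ = 4.87 on 1 and 78 df; power 58.6%.
- Six age bands: R² = 0.09 × 0.937 = 0.0843, λ = 7.37 on 5 and 74 df; power 49.1%.

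The two-group loss comes from discarded information. The age-band loss comes almost entirely from the extra degrees of freedom.

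**4. All cases (power in %, loss in points).** Losses are taken from unrounded powers and cover the four two-group splits and the six bands.

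| n | ρ | Continuous | 50/50 | 80/20 | Six age bands | Loss |
|---|---|---|---|---|---|---|
| 80 | 0.1 | 14.4 | 10.9 | 9.5 | 8.3 | 3.5 to 6.1 |
| 80 | 0.2 | 43.8 | 29.8 | 23.9 | 21.5 | 14.0 to 22.2 |
| 80 | 0.3 | 79.3 | 58.6 | 47.5 | 49.1 | 20.7 to 31.8 |
| 80 | 0.4 | 97.1 | 84.5 | 73.1 | 81.0 | 12.6 to 24.0 |
| 80 | 0.5 | 99.9 | 97.0 | 91.0 | 97.4 | 2.5 to 8.9 |
| 40 | 0.1 | 9.5 | 7.8 | 7.2 | 6.5 | 1.7 to 3.0 |
| 40 | 0.2 | 24.2 | 16.9 | 14.1 | 11.7 | 7.3 to 12.5 |
| 40 | 0.3 | 49.2 | 33.0 | 26.3 | 23.3 | 16.1 to 25.9 |
| 40 | 0.4 | 76.7 | 54.6 | 43.6 | 43.5 | 22.1 to 33.2 |
| 40 | 0.5 | 94.5 | 76.5 | 63.4 | 70.0 | 18.0 to 31.1 |

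Three equal age bands, tried as a milder grouping, lose 1.9 points at n = 80 and ρ = 0.5.

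**5. Simulation check.** There were 4,000 runs per setting. DAS28 was normal with mean 4.6, 5.0 or 5.6 and SD 1, truncated at 3.2 and cut at 5.1. Age was normal with mean 55 and SD 12, in the six bands. Losses at ρ = 0.2, 0.3 and 0.4 were 12.8 to 21.8, 19.1 to 29.2 and 11.4 to 17.4 points at n = 80. At n = 40 they were 5.7 to 12.0, 14.4 to 24.8 and 20.2 to 30.3 points. Together with the table, this gives about 6 to 33 points over ρ = 0.2 to 0.4.

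**The case against.** **The coding is not stated.** A reader might infer that Table 10 will definitely use the six age bands and the 5.1 cut. The documents do not go that far. SAP 5.2 gives the bands only for the baseline table. SAP 3.5.3 says baseline characteristics go into the models without mentioning groups, and SAP 2.4 speaks of baseline measures. What stands against this objection is that both operative sentences say subgroups, and unspecified coding needs the same repair.

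**The calculation is not the planned model.** It takes one modifier at a time, whereas SAP 5.6 plans multivariate models. The powers above are therefore not the power of Table 10. This stands.

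**Severity groups serve a purpose.** Protocol 7.0 says Korean reimbursement covers both moderate and severe RA and asks for evidence in moderate patients. That is a good reason to show the group means, but not to base the test on the cut. Nor is the use of DAS28 in SAP 5.5 a contradiction, because Tables 9.1 and 9.2 answer a different objective.

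**Other analyses look at who improves.** A reader might take Table 10 as the only one. Protocol 9.7.3 rules that out: it also plans analyses by severity level, disease-duration quartile and up to two further subgroups.

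**The gain has limits.** Continuous power is still only 44% at ρ = 0.2 with n = 80, and 49% at ρ = 0.3 with n = 40. The follow-up and baseline forms ask for DAS28 only if calculated, although eligibility itself requires a baseline value. The SAP's single DAS28 formula also differs from the protocol's CRP version. A non-linear relation could favour groups.

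**Conclusion.** The point holds as a minor improvement to an exploratory analysis. Both documents word the modifier test by subgroup and leave the cut-points open. If age and severity are grouped, the relation is linear and one modifier is tested at a time, the loss is about 6 to 33 points of power at ρ = 0.2 to 0.4 across n = 80 and n = 40. It is about 2 to 6 points at ρ = 0.1 with either n, and about 2 to 9 at ρ = 0.5 with n = 80. At ρ = 0.5 with n = 40 it is larger, 18 to 31 points for the two-group splits and six bands. Grouping gained power in none of the settings computed, all of which are linear. The range should not be quoted without these conditions: the documents give no correlation, distribution or effect-modification size, claim no power here, and contain no figure that this contradicts.

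**What to change.** In SAP 5.6 (Table 10) and Protocol 9.7.8, state that age in years and baseline DAS28 enter the models as continuous terms, one degree of freedom each. Report each slope with its 95% confidence interval, per 10 years and per 1 DAS28 point. Add a quadratic term as a limited check of linearity. Keep the age-band and moderate/severe means as descriptive rows, with the bands fixed in advance.

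The cost is a sentence in each document and a new row layout in Table 10, with no new data. The DAS28 formulas in Protocol 9.2.4.7 and SAP 3.5.2 have to be reconciled first, since the slope per DAS28 point depends on the scale. The statistical downside is the linearity assumption, which the quadratic term checks only weakly with 40 to 80 patients.
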